RA	Rheumatoid arthritis
RA-FQ	Rheumatoid Arthritis Flare Questionnaire
RAID	Rheumatoid Arthritis Impact of Disease
SAE	Serious Adverse Event
SAP	Statistical analysis plan
SoA	Schedule of Activities
SDAI	Simple Disease Activity Index
csDMARD	Conventional Synthetic Disease-Modifying Anti-Rheumatic Drug
SF-36	36-Item Short-form Health Survey
SmPC	Summary of Product Characteristics
SC	Subcutaneous
SUSAR	Suspected Unexpected Serious Adverse Reaction
TDM	Therapeutic drug monitoring
TNF α	Tumor necrosis factor inhibitor
tsDMARD	Targeted synthetic Disease-Modifying Anti-Rheumatic Drug
VAS	Visual Analogue Scale
WPAI:RA	Work Productivity and Activity Impairment Questionnaire: Rheumatoid Arthritis

1. Protocol Summary

[figure not shown]
1.1. Synopsis

The Rheumatoid Arthritis therapeutic DRUG Monitoring trial RA-DRUM

Protocol Title	A multi-center, open, randomized, 18-month, parallel-group, superiority study to compare the effect of proactive therapeutic drug monitoring versus standard of care with regards to maintenance of sustained disease control without flares in adults with rheumatoid arthritis treated with a subcutaneous tumor necrosis factor inhibitor
Brief Title	Effect of proactive therapeutic drug monitoring on maintenance of sustained disease control in adults with rheumatoid arthritis on a subcutaneous TNF inhibitor: The Rheumatoid Arthritis therapeutic DRUG Monitoring trial (RA-DRUM)
Rationale	There is a considerable variation in serum drug levels among rheumatoid arthritis (RA) patients on tumor necrosis factor inhibitors (TNFi), and a high number develop neutralizing anti-drug antibodies (ADAb). Sub-therapeutic drug levels and ADA formation are major contributors to TNFi treatment failure and disease flare. Proactive therapeutic drug monitoring (TDM), i.e., individualized drug dosing based on regular assessments of serum drug levels and ADA, has the potential to optimize the efficacy and safety of TNFi treatment. The Norwegian Drug Monitoring (NOR-DRUM) B study (JAMA 2021) showed that proactive TDM reduced the occurrence of flares in patients with immune-mediated inflammatory disease using infliximab, an intravenously administrated TNFi. Different administration routes and molecular structures limit the opportunity to extrapolate results from TDM of infliximab therapy to treatment with subcutaneous (SC) TNFi, and there is a need for trials investigating the efficacy of proactive TDM for SC TNFi.
Objectives	
Primary objective: To assess whether TDM is superior to standard of care in order to maintain sustained disease control without flares in patients with RA treated with SC TNFi.
 
Secondary objectives:
 
 • To compare effectiveness of proactive TDM to standard of care applying different outcome measures • To assess safety of proactive TDM • To assess whether proactive TDM influences drug survival, drug consumption, occurrence of ADA and serum drug levels
Endpoints	
Primary endpoint: Sustained disease control over the follow-up period of 18 months without flare, with flare defined as either of the following:
 
 • A combination of an increase in Disease Activity Score using 28 joints C-reactive protein (DAS28-CRP) > 1.2, or > 0.6 if DAS28-CRP ≥ 3.2, AND ≥ 2 swollen joints on examination of 44 joints

	
 • Consensus between patient and physician that a disease flare has occurred, leading to a major change in treatment 
If more than one TNFi type are included, subgroup analyses according to each TNFi type used will be performed.
 
Secondary endpoints:
 
 • Disease activity at 4, 8, 12, and 18 months assessed by DAS28-CRP, Evaluators Global Assessment of Disease Activity (EGA), Clinical Disease Activity Index (CDAI), Simple Disease Activity Index (SDAI), American College of Rheumatology (ACR)/European Alliance of Associations for Rheumatology (EULAR) remission criteria, Rheumatoid Arthritis Impact of Disease (RAID), Modified Health Assessment Questionnaire (MHAQ), biochemical parameters • Time to disease flare • Number and type of adverse events (AEs) • Drug survival, drug consumption, occurrence of ADAbs, serum drug levels
Overall Design	
A multicenter, randomized, two-arm, parallel-group, open, superiority trial where adult participants with RA in DAS28-CRP remission or low disease activity (DAS28-CRP < 3.2) on therapy with standard dose of a SC TNFi (adalimumab) for 3-24 months with indication for continuation of treatment according to the treating physician are stratified by country and allocated 1:1 to:
 
 • Administration of TNFi based on proactive TDM (TDM group) • Administration of TNFi based on standard of care without knowledge of serum drug levels or ADAbs status (Standard of care group) 
The protocol has been developed with the aim of including RA patients on therapy with adalimumab. If sufficient evidence emerges regarding therapeutic ranges of other SC TNFi during the study period, it will be considered to amend the protocol to include RA patients on other SC TNFi.

Visit Frequency	Onsite visits will be conducted at 0, 4, 8, 12, and 18 months following randomization, with additional digital visits and blood sampling at 2, 6, 10, 14, and 16 months.
Study Duration	18 months
Number of Participants	A minimum of 350 patients will be enrolled.

1.2. Schema

Created with BioRender

DAS28-CRP = Disease Activity using 28 joints C-reactive protein; **RA** = rheumatoid arthritis; **SC** = subcutaneous; **TNFi** = Tumor Necrosis Factor Inhibitors

1.3. Schedule of Activities (SoA)

Procedure	Screening	Intervention Period (visit month/visit no)										E/D	Extra Visit	Notes
		Baseline*	2	4*	6	8*	10	12*	14	16	18*			
		Visit 1	Visit 2	Visit 3	Visit 4	Visit 5	Visit 6	Visit 7	Visit 8	Visit 9	Visit 10			
Informed consent	X													
Inclusion and exclusion criteria	X	X												See Sections 5.1 and 5.2
Randomization		X												See Sections 6.3 and 9.3.1
Demography		X												See Section 8.1.1
Height and weight		X												See Section 8.1.1
Medical history including tobacco use		X												See Section 8.1.1
Current medical conditions		X												See Section 8.1.1
Routine laboratory tests		X		X		X		X			X	X	X	Hemoglobin, platelet count, white blood cells with differentials, ALT, creatinine, CRP, ESR. See Section 8.3.1
Biobank full blood		X												All sites See Section 8.1.2
Biobank**		X		X		X		X			X	X	X	Full blood, plasma and serum See Section 8.1.2
Assessment of disease activity		X		X		X		X			X	X	X	DAS28-CRP, EGA, 44 joint count, CDAI, SDAI See Section 8.2.1
Assessment of drug levels and ADAb***		X	X	X	X	X	X	X	X	X	X	X	X	See Section 8.5

RA-FQ, EQ-5D, WPAI:RA		X	X	X	X	X	X	X	X	X	X	X	X	X	See Sections 8.2.1 and 8.8
SF-36, MHAQ, RAID		X		X		X		X		X	X	X	X	X	See Sections 8.2.1 and 8.8
Record of concomitant medication for RA		X		X		X		X		X	X	X	X	X	See Section 6.9.2
AE registration		X		X		X		X		X	X	X	X	X	See Section 10.3
Adherence		X	X	X	X	X	X	X	X	X	X	X	X	X	By questionnaires and digital calendar See Section 6.5
	
*Onsite hospital visits ** Participants at Diakonhjemmet Hospital only ***In all participants AE = Adverse Events; ALT=Alanine Transaminase; E/D = Early Discontinuation; EGA = Evaluators Global assessment of disease activity; ESR= Erythrocyte sedimentation rate; EQ-5D = European Quality of Life 5 Dimensions; Ex visits = Extra visit if flare; CDAI = Clinical disease activity index; CRP= C-reactive protein; DAS28-CRP = Disease Activity Score using 28 joints C-reactive protein; MHAQ = Modified Health Assessment Questionnaire; PGA = Patient Global assessment of disease activity; RAID = Rheumatoid Arthritis Impact of Disease; RA-FQ = Rheumatoid Arthritis Flare Questionnaire; SDAI = Simple disease activity index; SF-36= 36-Item Short-form health survey; WPAI:RA = Work Productivity and Activity Impairment Questionnaire: Rheumatoid Arthritis
														

2. Introduction

This protocol outlines the RA-DRUM (Rheumatoid Arthritis therapeutic DRUG Monitoring) trial, a randomized controlled trial that aims to optimize therapy for patients with RA using SC TNFi. RA imposes a significant burden on patients, healthcare systems, and society (1). The proposed study will assess if individualizing treatment by TDM can improve the effectiveness of SC TNFi in maintaining disease control for patients with RA.

2.1. Study Rationale

TNFi are used worldwide, with adalimumab as one of the most used medical compounds overall in 2022 (2). TNFi, including adalimumab, have revolutionized the treatment of prevalent chronic immune-mediated inflammatory diseases, including RA (2-4). However, a significant proportion of RA patients either do not respond adequately to initiated therapy or lose treatment effect over time (5, 6). Disease flares can negatively impact quality of life and can lead to irreversible joint damage, prevention of flares is thus important in management of RA (1). Observational data have shown extensive individual variation in serum drug levels among patients on standard doses of adalimumab and other SC TNFi, suggesting both under- and overtreatment of a substantial proportion of patients (7-9). Additionally, TNFi and other therapeutic antibodies can elicit an immune response in the patient. Many patients develop anti-drug antibodies (ADA) during therapy, contributing to reduced drug levels and increasing the risk of drug reactions (10). By individualizing therapy, i.e., reducing under-and over treatment and in guiding treatment decisions, TDM is a tool that can be used to optimize the effectiveness of TNFi treatment, making it a topic of great interest to clinicians nationally and internationally (11).

The RA-DRUM study is the first trial to evaluate the effect of TDM in patients with RA treated with SC TNFi. It will provide important insights, aiming to contribute to the realization of a personalized medicine approach for TNFi therapy. The results of this study could also impact healthcare economics, as the high costs of TNFi restrict their use (12). Moreover, RA-DRUM presents unique opportunities for translational research on the poorly understood area of genetic and immunological mechanisms underlying drug immunogenicity (10). Further identification of predisposing genetic markers that could serve as predictors of loss of response is highly relevant to individualize treatment with biological drugs (13).

While a personalized medicine approach to SC TNFi by TDM seems reasonable, the effectiveness of such a treatment strategy in the management of RA with regard to sustained disease control remains to be shown in a randomized controlled trial like the RA-DRUM trial.

2.2. Background

2.2.1. Treatment of RA

RA is characterized by symmetric inflammation of the peripheral joints (14). The high burden of disease in RA is related both to symptoms of active inflammation and to the subsequent development of irreversible joint damage (15). The overarching treatment goal is early and aggressive suppression of inflammation, and maintenance of remission or low disease activity to prevent structural damage and disability (16). TNFi are widely used antibody-based drugs

targeting TNF and are usually added if the treatment target is not achieved with a csDMARD, such as methotrexate (16). The introduction of TNFi around year 2000 played a significant role in making remission an achievable treatment goal in RA (3). However, more than half of patients lose efficacy over time (17, 18). A failure to maintain disease control has a major negative impact on patients' quality of life and puts the individual at risk of developing serious organ damage and disability (19, 20). Loss of treatment effect can be due to underexposure to the drug (21).

2.2.2. Serum Drug Levels and ADAbs

Therapy with SC TNFi and other biological drugs are not currently personalized, but prescribed in a uniform manner to all patients. Observational studies have shown associations between serum drug levels and effectiveness and also revealed considerable inter-individual variation in serum drug levels for TNFi, indicating both under- and overexposure (7-9, 22, 23). Therapeutic ranges, i.e., serum levels expected to achieve the desired therapeutic effects, have been identified for adalimumab and other TNFi (7, 22-24). A considerable proportion of patients on standard dose have serum levels above or below the therapeutic range, indicating a potential for dose-optimization. One major reason for the large variation in serum drug levels is the development of ADAbs which are formed as part of immune responses to TNFi and other biological drugs, which are large, complex and allogenic proteins (10). ADAbs influences the pharmacokinetics of the drug either by direct binding to the target binding site of the therapeutic antibody (neutralizing ADAbs) or by forming immune complexes with the drug resulting in altered clearance (non-neutralizing ADAbs). ADAbs production has proved to be a significant clinical problem. Low levels of ADAbs might be transient, but high levels of ADAbs reduce the effect of the drug and decrease serum drug levels (25, 26). Drug holidays or low-dose regimens have been shown to predispose to ADAbs formation (27). Patients with RA may be more prone to ADAbs formation than patients with other immune-mediated inflammatory diseases (27). Immunosuppressive co-medication, in particular methotrexate, is protective with a reduction of ADAbs formation by up to 40% (25, 26, 28, 29). Whereas the precise immunological mechanisms leading to ADAbs formation remains unknown, knowledge regarding predisposing genetic factors including HLA are increasing (13, 21, 30).

2.2.3. Therapeutic Drug Monitoring

Proactive TDM, a personalized treatment strategy based on regular assessments of serum drug levels and ADAbs and adjustments in drug dose to keep serum drug levels within the defined therapeutic range, has been proposed as a clinical tool to optimize efficacy, patient safety and cost-effectiveness of TNFi treatment (11). A treatment strategy based on proactive TDM may improve TNFi therapy by:

- i) Minimizing drug underexposure, which might lead to loss of response
- ii) Reducing drug overexposure, which predispose patients to side effects and increases costs
- iii) Allowing for timely identification of ADAbs development, with the possibility to prevent treatment failures prior to a clinical flare

Methods for assessment of serum drug levels and ADAbs are available for use in clinical practice (21). Guidelines and recommendations for implementation of TDM in standard care of patients on treatment with biological drugs are needed as the use of therapeutic monoclonal

antibodies are rapidly increasing (16, 31). However, due to limited high-grade evidence with regard to clinical utility and cost-effectiveness of TDM, treatment recommendations are inconclusive, and TDM has yet to gain widespread use within rheumatology. The need for prospective studies comparing TDM with usual care, is also highlighted in the research agenda of the recent EULAR points to consider for TDM in rheumatology (31).

The NORwegian DRUG Monitoring (NOR-DRUM) trials, two randomized controlled trials across a range of IMIDs, demonstrated that TDM improved efficacy during maintenance-, but not during induction therapy with one TNFi, infliximab (32, 33). In these trials, proactive TDM resulted in a nearly 20% reduction in flare without increased infliximab consumption compared to usual care during maintenance therapy. Showing proof of principle of effectiveness of a TDM-based treatment strategy for infliximab, easily assessed due to its intravenous administration, was very important. Having established the benefit of TDM in principle, we now aim to determine if proactive TDM also is a viable, practical tool across the other TNFis, which are administered SC.

Proving a benefit of TDM for SC TNFi will be a strong point in favor of TDM implementation into treatment guidelines, and can be expected to have a particularly strong impact on the medical community treating RA patients.

As adalimumab is currently by far the most used SC TNFi and since knowledge of the therapeutic ranges is at this time most robust for adalimumab, this protocol has been developed with the aim of including RA patients on therapy with adalimumab. Should evidence regarding therapeutic ranges emerge and the clinical use of other SC TNFi increase during the study period, RA patients on other SC TNFi will be considered for inclusion following a protocol amendment.

2.3. Benefit/Risk Assessment

Participants are already on prescribed therapy with the investigational medicinal product (IMP) adalimumab, and the drug is continued in both groups. More detailed information about the known and expected benefits and risks and reasonably expected AEs of adalimumab can be found in the Summary of Product Characteristics (SmPC).

2.3.1. Risk Assessment

Investigational intervention: Patients are already on therapy with the IMP, no patients will start with a new drug as a consequence of study inclusion. During the conduct of the trial, some patients might change therapy due to findings of ADAbs, but this we expect to be beneficial to the patient in that they may avoid a possible clinical flare (34). The IMP is used for an approved indication. The investigational intervention is not expected to increase the risk of AEs from the medication during the study. This includes participants with a dose decrease or increase due to the TDM strategy as treatment effectiveness and AEs are expected to be related to drug levels, i.e., the amount of pharmacologically active drug in the circulation, and not the dose.

Study design: Participants in both groups will use slightly more time at each clinical visit compared to usual clinical care due to clinical evaluation by the blinded joint assessor. They

will have to fill in PROs every second month. Except for blood sampling, which is also performed regularly in usual clinical care, there are no invasive procedures in this study.

Mitigation Strategy

Study personnel will receive adequate training. User representatives have participated in the protocol development and will be involved in the preparations for the practical conduct of the study, to ensure the participants' interests and preferences are adequately considered.

Participants will receive close follow-up from a physician and study nurse in the study and will be given the opportunity for a rapid extra assessment if a suspected disease flare occurs. If the participant does not respond to the treatment, the investigator can switch treatment regardless of study arm and without consequence for further study participation. Patients can withdraw from the study at any time.

2.3.2. Benefit Assessment

For the individual participant

Each participant will receive close follow-up. The follow-up will ensure careful and standardized assessment of treatment effects and AEs. In case of suspected disease flare, regardless of treatment group, the participant will be offered an extra assessment and necessary adjustment of treatment within a short time. The participant will contribute to knowledge within a clinically important field with current knowledge gaps.

For the group of participants

The results of RA-DRUM are expected to have significant implications for the use of adalimumab and other SC TNFi. Inadequate treatment effect and loss of effect over time is a major problem in the treatment of patients with a range of chronic immune-mediated inflammatory diseases such as RA. If RA-DRUM shows that individualized therapy based on TDM can improve treatment and/or result in fewer side effects, this study could contribute to more optimal drug treatment. This will have significant implications for patients with a range of immune-mediated inflammatory diseases.

For society

The economic burden of biological treatment is formidable. If it is possible to improve cost-effectiveness, these expensive drugs could become available to more patients. If the drugs are used more effectively, the climate footprint may also be reduced.

For science

The genetic and immunological mechanisms underlying the development of ADAbs are not known but are believed to be linked to certain hereditary factors (HLA). This large, well-characterized cohort of patients will be able to contribute to translational research and generate new knowledge within this important area.

2.3.3. Overall Benefit Risk Conclusion

Considering the measures taken to minimize risk to the participants in this study, the potential risks identified in association with proactive TDM are justified by the anticipated benefits that may be afforded to patients with RA.

3. Objectives and Endpoints

Objectives	Endpoints	Assessments
Primary		
To assess whether proactive TDM is superior to standard of care in order to maintain sustained disease control without flares in patients with RA treated with SC TNFi.	
Sustained disease control over the follow-up period of 18 months without flare, with flare defined as either of the following:
 
A combination of an increase in Disease Activity Score using 28 joints- C-reactive protein (DAS28-CRP) > 1.2, or > 0.6 if DAS28-CRP ≥ 3.2, AND ≥ 2 swollen joints on examination of 44 joints
 
Consensus between participant and physician that disease flare has occurred, leading to a major change in treatment*
 
*A major change in treatment includes switching to another biological disease-modifying anti-rheumatic drug (bDMARD) or targeted synthetic disease-modifying anti-rheumatic drug (tsDMARD), adding a conventional synthetic disease-modifying anti-rheumatic drug (csDMARD), increasing the dose of a concomitant csDMARD, i.e., methotrexate increased by ≥ 5 mg/week, adding or increasing systemic glucocorticoids (per orally, intravenous, or intramuscular), and receiving more than one intra articular glucocorticoid injection at one visit. If the dose of TNFi is increased for clinical reasons (Standard of care group), this should also be regarded as a major change in treatment.
	
 • DAS28-CRP • Joint count of 44 joints

	Subgroup analyses of the primary endpoint according to each TNFi type (if more than one TNFi type will be included)	
Secondary		
To compare effectiveness of proactive TDM to standard of care on different outcome measures	Disease activity at 4, 8, 12, and 18 months Time to disease flare (as defined above)	
 • DAS28-CRP • Joint count of 44 joints • Patient Global assessment of disease activity (PGA) • Evaluator Global assessment of disease activity (EGA) • Clinical Disease Activity Index (CDAI) • Simple Disease Activity Index (SDAI) • Rheumatoid Arthritis Impact of disease (RAID) • Modified Health Assessment Questionnaire (MHAQ) • ACR/EULAR remission criteria • Biochemical parameters (C-reactive protein (CRP) and erythrocyte sedimentation rate (ESR))
Safety	Number and type of adverse events (AE)	
 • Assessments of AE
To assess whether proactive TDM influences drug survival, drug consumption, occurrence of ADAbs, serum drug levels	Drug survival, drug consumption, occurrence of ADAbs, serum drug levels	
 • Assessments of drug consumption • Drug survival • Assessments of serum drug levels and ADAbs

Explorative/Other Objectives	

 • To assess cost effectiveness, utility, and impact on quality of life of proactive TDM compared to standard of care • To assess whether biomarkers (including genetic markers) and other factors can predict development of ADAb in participants on SC TNFi • To study how serum drug levels and ADAb are associated with drug efficacy and safety • To study predictors of flare and treatment response • To study differences in immunogenicity between different SC TNFi • To characterize anti-drug immune responses, including ADAbs isotypes, epitopes, and association to genetic markers (e.g., HLA) • To assess how TDM influences treatment with respect to serum drug/ADAbs levels and disease activity • To assess efficacy of TDM in the subgroup of participants with ADAbs • To study feasibility of TDM and compliance to the treatment algorithm • To study the performance of the treatment strategy within the group of participants affected by the algorithm • To study the effect of dose escalation/decrease on serum drug levels and clinical outcomes • To study the value of TDM in the setting of switching of drug to a different bDMARD • To study effectiveness of TDM in subgroups of participants where TDM is assumed to be particularly valuable, including participants with high disease activity at baseline, participants not on immunosuppressive co-medication, and participants with previous secondary loss of effect of TNFi • To study adherence • To study corticosteroid consumption • To study different measures for assessing flares 	
 • European Quality of Life 5 Dimensions (EQ-5D, 36-Item Short-form health survey (SF-36), Work Productivity and Activity Impairment Questionnaire: Rheumatoid Arthritis (WPAI-GH) • Genetic markers and biomarkers • Assessments of serum drug levels and ADAbs • Assessments of AE • DAS28-CRP, Joint count of 44 joints, PGA, EGA, CDAI, SDAI, RAID, MHAQ, ACR/EULAR remission criteria • Biochemical parameters (including CRP and ESR) • Drug survival • Adherence questionnaire • Drug calendar • Co-medication assessment • Rheumatoid arthritis flare questionnaire (RA-FQ)

4. Study Design

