5.5. Criteria for Temporarily Delaying

Not applicable.

6. Study Intervention and Concomitant Therapy

Study interventions are all pre-specified investigational and non-investigational medicinal products, medical devices, and other interventions (e.g., surgical and behavioral interventions) intended to be administered to the study participants during the study conduct.

Participants enrolled in the RA-DRUM trial are on therapy with SC TNFi.

They are randomized 1:1 to either:

- Administration of SC TNFi based on proactive TDM (TDM group)
- Administration of SC TNFi according to standard of care without knowledge of serum drug levels or ADAb status (Standard of care group)

If the participants are using prednisolone (≤ 7.5 mg prednisolone oral dose or equivalent) or concomitant csDMARD including methotrexate, sulfasalazine, hydroxychloroquine, or leflunomide in any dose this will be continued in an unchanged dose.

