6.1. Study Intervention Administered

6.1.1. The TDM Group

In the TDM, the SC TNFi dose will be adjusted according to the algorithms outlined in Table 1 in order to keep the drug level within the therapeutic range.

Prior to a dose change, the study personnel must check by a phone call to the participant if the drug has been administered according to the treatment algorithm (as defined in Table 1) or if injections have been postponed or dropped due to medical or other reasons.

The following exceptions from the algorithm in Table 1 are recommended if the drug has not been administered according to the treatment algorithm during the last month:

- If the drug level is low with no or low ADAb and there has been a pause in medication of more than 1 week for the last month prior to the blood sampling the dose should be kept stable
- If the drug level is high and the participant has taken the injection in a higher dose or more frequent than prescribed, the dose should be kept stable.

The reason for pause in therapy should be recorded in the eCRF.

In the TDM group, results for drug levels and ADAb will be reported to the investigators via the eCRF within 10 days after receiving the sample. Results in the standard care group will be recorded in the eCRF but not accessible to study personnel, and transferred to the PI upon conclusion of the clinical trial.

Table 1. Study Intervention

	Adalimumab	x	y	z
Trade name(s)	Originator and all approved adalimumab biosimilars*			
Type	Biologic drug			
Dose Formulation	Subcutaneous (SC) injection			
Recommended Dose**	40 mg SC every 14 days, if necessary 40 mg SC every 7 days or 80 mg SC every 14 days			
IMP and NIMP	IMP			
Drug target range	5.0-12.0 mg/L			
Cut-off ADAb high levels	> 50 µg/L			
TDM strategy				
• Within target range	Keep dose			
• Low drug levels, ADAb undetectable or low levels	Decrease dosing interval by one week to a maximum of 40 mg/week			
• Low drug levels, ADAb high levels	Switch to another therapy			
• High drug levels	Increase dosing interval by one week up to a maximum of 6 weeks			

* All adalimumab biosimilars approved by the European Medicines Agency
**According to the Summary of Product Characteristics (SmPC)
ADAb = anti-drug antibodies; TDM = Therapeutic drug monitoring

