8.2.2. Definition of Flare

A flare is defined as a combination of an increase in DAS28-CRP of 1.2 units, or 0.6 if DAS28-CRP \geq 3.2, AND at least 2 swollen joints on examination of 44 joints (39, 40, 53).

If a participant does not fulfil the formal definition, but experiences a clinically significant worsening, according to both the investigator and participant, that leads to a major change* in treatment, this should be considered as a flare but be recorded separately in the eCRF.

*A major change in treatment includes:

- Switching to another bDMARD or a tsDMARD
- Adding a csDMARD
- Increasing the dose of a concomitant csDMARD
- Adding or increasing systemic glucocorticoids (per orally, intravenous or intramuscular)
- Receiving more than one intra-articular glucocorticoid injection at one visit
- Shortening the interval of the SC TNFi for clinical reasons (Standard of care group)

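### Sections 3 and 8.2.2 define the treatment change behind a consensus flare differently, and both count a clinically motivated TNFi increase only in the standard-of-care arm

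*Protocol*

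**What the plan says.** Flare has two limbs. One is a DAS28-CRP increase with at least two swollen joints of 44. The other is agreement between participant and physician that a flare has occurred, leading to a major change in treatment. That change is defined in Section 3 (Objectives and Endpoints) and again in Section 8.2.2 (Definition of Flare).

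- **csDMARD.** Section 3: "increasing the dose of a concomitant csDMARD, i.e., methotrexate increased by" at least 5 mg/week. Section 8.2.2: "Increasing the dose of a concomitant csDMARD", with no threshold. Section 6 lets participants continue "concomitant csDMARD including methotrexate, sulfasalazine, hydroxychloroquine, or leflunomide in any dose".
- **TNFi.** Section 3: "If the dose of TNFi is increased for clinical reasons (Standard of care group), this should also be regarded as a major change in treatment". Section 8.2.2: "Shortening the interval of the SC TNFi for clinical reasons (Standard of care group".
- **DAS28-CRP.** Section 3 and the Synopsis require an increase above 1.2. Section 8.2.2 has "a combination of an increase in DAS28-CRP of 1.2 units".

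Section 6.9.2 refers to Section 3, but only for changes in concomitant treatment. Section 8.2.2 does not defer to Section 3.

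Table 1 gives the recommended adalimumab dose as 40 mg every 14 days, "if necessary 40 mg SC every 7 days or 80 mg SC every 14 days". In the TDM group, a low level without high ADAb leads to: "Decrease dosing interval by one week to a maximum of 40 mg/week". Section 2.3.2 promises an extra assessment and any needed treatment adjustment after a suspected flare in either group.

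**The concern.** The binary flare-free endpoint carries the only hypothesis test (Sections 9.1 and 9.1.1), so its definition should be single and the same in both arms.

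First, with two lists, the same participant may be a flare at a site that follows one section and flare-free at a site that follows the other.

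Second, the TNFi item depends on the arm. The words about clinical reasons already leave out changes driven purely by the TDM algorithm. What the arm label removes in addition is a TDM increase made because participant and physician agreed that the disease had worsened. In standard of care that event is a failure. Only the joint count is blinded (Section 6.4), so blinding does not protect the consensus limb.

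**Working it through.** **1. The two lists, item by item.** Four items agree: switch to another bDMARD or a tsDMARD, added csDMARD, added or increased systemic glucocorticoid, and several joint injections at one visit. The differences are:

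| Event, with an agreed worsening | Section 3 | Section 8.2.2 |
|---|---|---|
| Methotrexate raised by less than 5 mg/week | Not counted as written | Counted |
| Sulfasalazine, hydroxychloroquine or leflunomide raised | Unclear | Counted |
| TNFi interval shortened, standard of care | Counted | Counted |
| Larger TNFi dose at unchanged interval, standard of care | Counted | Unclear |
| TNFi increased, TDM | Not listed | Not listed |

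Separately, a DAS28-CRP increase of exactly 1.2 fails under Section 3 and passes under Section 8.2.2. The wording for the 0.6 step differs in the same way. Both matter only at exact equality.

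**2. Who is affected by the arm label.** A TDM participant with an agreed worsening, without the DAS28-CRP plus swollen-joint criterion, and with a TNFi increase as the only change. An in-range level means that the dose is kept, and every other listed change made for an agreed flare counts in both arms.

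**3. Direction.** For this item, events can go uncounted only in TDM. Another item can work the other way. Table 1 prescribes a switch for a low level with high ADAb in TDM, while levels and ADAb are hidden in standard of care (Section 6.1.2). Such a switch would count as a flare if it coincided with an agreed worsening.

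**4. Size, as an illustration only.** The protocol gives no figure for the affected share, so it is an assumption, q.

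Inputs from Section 9.5: 72.5% flare-free in standard of care, at least 350 participants and 10-15% drop-out; 1:1 allocation is from Section 6.3. Per arm: 350/2 = 175 with no drop-out, 175 × 0.90 = 157 at 10% and 175 × 0.85 = 149 at 15%.

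The plan's own figure first. For 72.5% against 85% at 80% power, n per arm = (1.960 + 0.842)² × (0.725×0.275 + 0.85×0.15) / 0.125² = 7.849 × 0.3269 / 0.015625 = 164.2, so 165 per arm and 330 in total, as in Table 2. The pooled-variance formula gives 167 per arm, 334 in total.

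Now assume no true effect: 72.5% flare-free in both arms under an arm-neutral rule. Observed proportions are then 0.725 and 0.725 + q, and

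P(false superiority) = 1 − Φ(1.960 − q/SE), with SE = √{[0.725×0.275 + (0.725+q)(0.275−q)]/n}.

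For q = 0.02 and n = 175: SE = √[(0.1994 + 0.1900)/175] = 0.0472, q/SE = 0.424, and 1 − Φ(1.536) = 0.062.

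| q (net share) | n = 175 | n = 157 | n = 149 |
|---|---|---|---|
| 0 | 2.5% | 2.5% | 2.5% |
| 1 point | 4.0% | 3.9% | 3.9% |
| 2 points | 6.2% | 6.0% | 5.8% |
| 3 points | 9.3% | 8.8% | 8.5% |
| −1 point | 1.5% | 1.5% | 1.6% |

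Exact binomial enumeration with an unadjusted logistic Wald test gives 4.0, 6.2 and 9.3% at n = 175 for 1, 2 and 3 points. Each point of q moves the observed difference by one point, against a planned 12.5. At 175 per arm, 1 to 3 points is about 2 to 5 TDM participants (1.75 to 5.25).

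**The case against.** **The arm label has a design reason.** TDM dosing follows the algorithm, so a TDM increase is normally the intervention at work, whereas clinicians in standard of care see no levels and escalate on clinical grounds. Sections 4.1 and 6.1.3 also describe the TDM increase as following a flare already classified. This explains the label, but does not say how to classify an agreed worsening whose only treatment change is that increase.

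**The lists are not exhaustive.** Both open with the verb includes, and the protocol elsewhere uses dose for interval changes. A reader might infer that Section 8.2.2 excludes a larger dose at an unchanged interval; the text makes it unclear and no more. In the same way, the arm asymmetry is the natural reading and not an express rule.

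**Most cases could be recovered.** Section 8.2.2 has consensus flares recorded separately, Section 6.9.2 has RA medication changes documented, and it points to Section 3 for concomitant drugs. This narrows the csDMARD problem. It leaves the TNFi item open, and a medication record alone does not show whether a worsening was agreed.

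**An arm-neutral rule is not free of asymmetry.** If every increase after an agreed worsening counts, even with a low level, an automatic algorithm step completes the flare definition in TDM only. This stands, and the mixed cases need a rule set in advance.

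**Conclusion.** The point holds as a defect of definition in the primary endpoint. The two sections differ on the csDMARD threshold, on how the TNFi change is described and on the inequality sign. The clear conflict is a methotrexate increase below 5 mg/week; other csDMARDs and a larger TNFi dose at an unchanged interval are left unclear. Both sections also make the TNFi item depend on arm where the stated reason would suffice.

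A reader might infer that the trial is biased towards TDM, or that its false-superiority rate is 6 or 9%. The documents support neither. The affected group is narrow, its share is unknown, and ADAb-prompted switches could offset it. The rates of about 4, 6 and 9% (or about 1.5% for a net shift of 1 point the other way) rest on an assumed net share, no true effect and 72.5% flare-free in both arms. They show only that a few participants would matter. The unblinded consensus limb is disclosed in Sections 4.2 and 6.4 and is not an error in itself; it is a reason to keep the item independent of arm. The point should be fixed. Confidence is high on the wording and low on size.

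**What to change.** 1. Reconcile Sections 3 and 8.2.2 into one flare definition covering the type of TNFi change, csDMARD increases including drugs other than methotrexate, and the inequality signs, and let one section refer to the other. Which changes and thresholds count is for the sponsor to decide.
2. For endpoint classification only, define the TNFi item by the reason for the increase and not by arm. An increase made because of an agreed clinical worsening is classified the same way in both arms; an increase with no agreed worsening counts in neither.
3. Record in the eCRF, in both arms, whether a worsening was agreed, dated before the drug level from that visit is seen, and the reason for each increase. A level may arrive about 17 days after sampling (7 days' transport aim in Section 8.5 plus 10 days' reporting in Section 6.1.1), so link the increase to the recorded worsening and not to the same visit.
4. State in advance how TDM cases with both an agreed worsening and a low level are classified, and report a sensitivity analysis with them classified the other way.

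Cost: wording in two sections and one or two eCRF fields. A few more TDM flares may count, some from increases that the algorithm would have made anyway, and the reason is still judged unblinded. Care does not change.
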